9.2.2.3.4 Serious Adverse Events

Information on SAEs will be collected and assessed throughout the trial, from inclusion until 6 months after booster injection.

Any SAE occurring at any time during the trial will be reported by the Investigator through the EDC system and according to the completion guidelines provided by the Sponsor. All information concerning the SAE is to be reported, either as part of the initial reporting or during follow-up reporting if relevant information became available later (eg, outcome, medical history, results of investigations, copy of hospitalization reports). The Investigator will assess the causal relationship between the SAE and the investigational product as either “Not related” or “Related”, as described in [Section 10.4](#).

See [Section 10](#) for further details on SAE reporting.

9.2.2.3.5 Adverse Events of Special Interest

Serious AESIs

The following serious AESIs will be considered:

- Serious hypersensitivity/allergic reactions occurring in all subjects within 7 days after vaccination
- Serious viscerotropic disease occurring in all subjects within 30 days after vaccination
- Serious neurotropic disease occurring in all subjects within 30 days after vaccination
- Serious dengue disease requiring hospitalization^a occurring in all subjects at any time during the study

Specific guidelines are provided to the Investigator to help in the assessment of AEs that may be indicative of viscerotropic or neurotropic disease (see Guidelines for Assessing Viscerotropic and Neurotropic AE).

Non-Serious AESIs

The following non-serious AESI will be considered:

^a A hospitalized subject is any subject admitted to hospital with bed attribution or any healthcare institution and requiring in-patient care

- Hypersensitivity/allergic reactions occurring in all subjects within 7 days after vaccination.

9.2.2.3.6 Assessment of Causality

The Investigator will assess the *causal relationship* between each unsolicited systemic AE and vaccination as either not related or related, based on the following definitions^a:

- 0: Not related – The AE is clearly / most probably caused by other etiologies such as subject’s underlying condition, therapeutic intervention, or concomitant therapy; or the delay between vaccination and the onset of the AE is incompatible with a causal relationship; or the AE started before the vaccination (screening phase, if applicable)
- 1: Related – There is a “reasonable possibility” that the AE was caused by the vaccination, meaning that there is evidence or arguments to suggest a causal relationship

Note: By convention, all injection site AEs (solicited and unsolicited) and all solicited systemic reactions are considered to be related to vaccination and referred to as reactions, and therefore do not require the Investigator’s opinion on relatedness.

AEs likely to be related to the product, whether serious or not, that persist at the end of the trial will be followed up by the Investigator until their complete disappearance or the stabilization of the subject’s condition. The Investigator will inform the Sponsor of the date of final disappearance of the event.

9.2.2.4 Method for Assessing Virological Confirmation of Suspected Dengue Disease and Assessment of Disease Severity

In the event of a suspected hospitalized dengue case, the following tests will be performed based on the process described in below.

Dengue Screen RT-PCR

Dengue screen RT-PCR test will be performed by Sanofi Pasteur GCI, Swiftwater, USA or GCI designated laboratory.

Assessment and quantitation of dengue viremia is determined by testing serum samples with a nucleic-acid based assay. RNA is extracted from the serum to discard potential Taq polymerase inhibitors or interfering factors, using a commercial kit. Then, a RT-PCR is carried out with primers from a gene sequence conserved among dengue viruses. Due to a virus standard included in each run, results can be expressed as a concentration of log₁₀ plaque forming unit (PFU)/mL.

Simplexa Dengue RT-PCR

Serotype identification of post-infectious dengue viremia is determined by testing serum samples with a nucleic-acid based assay. Briefly, RNA is extracted from the serum to discard potential polymerase inhibitors or interfering factors, using a commercial kit. Then the Simplexa dengue RT-PCR assay is carried out which incorporates serotype-specific primers from dengue

^a ICH Guidelines, Clinical Safety Data Management E2A

sequences. The results are expressed qualitatively and reported for each dengue serotype as detected or not detected.

This assay will be used on all DS RT-PCR positive or Dengue NS1 Ag ELISA positive samples for serotype identification. In addition sequencing analysis may be attempted on isolates from the serotyped samples.

Dengue NS1 Ag ELISA

The NS1 Ag ELISA will be performed using a commercially available kit: “Platelia™ Dengue NS1 Ag” from Bio-Rad (Marnes-la-Coquette, France). The manufacturer’s instructions are followed. The Dengue NS1 Ag test is a one-step sandwich-ELISA based assay that enables detection of NS1 Ag in serum. The test uses murine monoclonal antibodies (MAbs) for capture and revelation. Samples and controls are directly and simultaneously incubated with the conjugate within the microplate wells coated with MAb. If NS1 Ag is present in the sample, an immune-complex MAb-NS1-MAb/peroxidase will be formed. The presence of immune-complex is demonstrated by addition of a chromogenic solution that initiates a color development reaction. After 30 minutes of incubation at room temperature, the enzymatic reaction is stopped by addition of an acid solution. The optical density (OD) reading obtained with a spectrophotometer set at 450/620 nm is proportional to the amount of NS1 Ag present in the sample. The presence of NS1 Ag in an individual sample is determined by comparing the OD reading of the sample to the OD of the cutoff control serum.

Sample ratios of < 0.5 , ≥ 0.5 to ≤ 1.0 , and > 1 will be indicative of negative, equivocal, and positive results, respectively.

Hematology – Biochemistry

Hematology and biochemistry parameters (hematocrit, platelet count, AST, and ALT) will be measured by local laboratories using standard methods as per routine standard of care in each country. However, the measurement of any of these biological parameters may be undertaken (or repeated), based on the Investigator’s judgment, to ensure the adequate evaluation of dengue disease severity. It is noteworthy that hematocrit and platelet counts are required parameters in the WHO/IDMC severity assessment protocol. The results will be collected in the eCRF.

The assessment of biological parameters will be: within normal range or outside normal range. Normal ranges for each biological parameter will be provided by the local laboratory and collected in the eCRF.

Interpretation of Results

If a sample is positive for the dengue screen RT-PCR (ie, \geq LLOQ) and/or the NS1 assay is positive and/or the Simplexa dengue RT-PCR is positive, this will be classified as a VCD infection.

9.2.3 Efficacy

No clinical efficacy data will be obtained in the trial.

9.3 Additional Endpoints and Assessment Methods

9.3.1 Immunogenicity

9.3.1.1 Immunogenicity Endpoints

STAGE I:

- Neutralizing Ab titers against each dengue virus serotype at all STAGE I time points
- Neutralizing Ab titers against FVs at baseline prior to first injection of CYD dengue vaccine (JE in the Philippines, YF in Colombia)

STAGE II:

- Neutralizing Ab titers against each dengue virus 28 days post booster injection (Y1 for subgroup a and Y2 for subgroup b)

AIT Subset Only:

The immune response against the 4 dengue serotypes elicited by the boosting dose of dengue vaccine will be assessed by the measurement of neutralizing antibodies, to include:

- 1) Neutralizing Ab response
 - a. Neutralizing Ab levels against each of the 4 parental dengue virus strains immediately prior to and at 7, 14, and 28 days post-booster injection
- 2) Ab specificity and affinity maturation
 - a. Heterotypic and homotypic serotype-specific neutralizing Ab responses will be assessed qualitatively immediately prior to and 28 days post-injection 3 (STAGE I); and immediately prior to and at 28 days post-booster injection as a priority, and at 7 and 14 days post-injection if necessary (STAGE II). Homotypic Abs for individual serotypes will be defined based on values above lower limits of quantitation for the neutralizing titer and % of Ab remaining following depletion.
 - b. Serotype-specific affinity (K_D , nM) and Ab concentration ($\mu\text{g/mL}$) will be measured against the parental wild-type strains in the sera immediately prior to and at 28 days post-injection 3 (STAGE I) and immediately prior to and at 28 days post-booster injection (STAGE II).
- 3) CMI responses

The specific B and T immune response against the 4 dengue serotypes elicited by the CYD dengue vaccine booster will be assessed by ELISPOT or flow cytometry, using intracellular staining and phenotyping

- a. T-cell response:
 - Cytokine secreting CD4 and CD8 T cells count immediately prior to the primary dose schedules (STAGE I) and immediately prior to and 7, 14, and 28 days after the Year 1 and Year 2 booster dose for a subset of subjects in Groups 1, 2, and 3.
 - T-cell subclasses (naïve, effector, central and terminally differentiated memory T cells) count immediately prior to the primary dose schedules (STAGE I), and

immediately prior to and 7, 14, 28 days after the Year 1 or year 2 booster dose for a subset of subjects in Groups 1, 2, and 3.

- Cytotoxic T-cell effector markers immediately prior to the primary dose schedules (STAGE I), and immediately prior to and 7, 14, and 28 days after the Year 1 or Year 2 booster dose for a subset of subjects in Groups 1, 2, and 3.
- b. B-cell response:
 - Ex vivo B-cells (plasmablast) count (measured by ELISPOT) immediately prior to the primary dose schedules and immediately prior to and 7 and 14 days after the Year 1 or Year 2 booster dose for a subset of subjects in Groups 1, 2, and 3.
 - Memory B-cells count (measured by ELISPOT) immediately prior to the primary dose schedules and immediately prior to and 28 days after the year 1 or year 2 booster dose for a subset of subjects in Groups 1, 2, and 3.

The assays, along with the corresponding samples, will be managed by the specific Sanofi Pasteur organization (eg, Research), or with an external laboratory, whichever applies.

9.3.1.2 Immunogenicity Assessment Methods

9.3.1.2.1 Flavivirus Neutralizing Abs

Japanese Encephalitis (JE) Neutralizing Abs

JE virus neutralizing Ab measurement will be assessed by PRNT by Sanofi Pasteur GCI, Swiftwater, USA, or a GCI outsourced laboratory. Serial 10-fold dilutions of serum to be tested (previously heat-inactivated) are mixed with a constant challenge dose (expressed as PFU/mL) of the JE Beijing strain (genotype III). The mixtures are inoculated into wells of a plate of confluent LLC-MK2 cells. After adsorption, cell monolayers are overlaid and incubated for several days. The reported value (end point neutralization titer) represents the highest dilution of serum at which $\geq 50\%$ of JE challenge virus is neutralized when compared to the negative control wells, which represents the 100% virus load. The LLOQ for this study will be 10 (1/dil).

JE Neutralizing Ab measurement will be assessed at V01 (BL1) only in subjects from the Philippines.

Yellow Fever (YF) Neutralizing Abs

YF neutralizing Ab levels will be measured using PRNT by Sanofi Pasteur GCI, Swiftwater, USA, or GCI outsourced laboratory. Briefly, serial two-fold dilutions of serum to be tested (previously heat-inactivated) are mixed with a constant concentration of the YF vaccinal strain 17D (expressed as PFU/mL). The mixtures are inoculated in duplicate into wells of a plate of confluent Vero cells. After adsorption, cell monolayers are overlaid and incubated for a few days. The reported value (end point neutralization titer) represents the highest dilution of serum at which $\geq 50\%$ of YF challenge virus (in plaque counts) is neutralized when compared to the negative control wells, which represents the 100% virus load. The LLOQ for this study will be 10 (1/dil).

YF Neutralizing Ab measurement will be assessed at V01 (BL1) only in subjects from Colombia.

9.3.1.2.2 Additional Immunology Testing

Blood samples will also be drawn from subjects randomly selected in the AIT subset. For evaluation of CMI, Ab specificity and affinity maturation, samples will be drawn from STAGE I subjects immediately before Injection 1 (specificity, affinity and CMI) and at 28 days after Injection 3 (specificity and affinity). During STAGE II, only subjects identified as seropositive at baseline and thus eligible to booster injection will continue to be part of the AIT subset. Sampling from these subjects will continue into STAGE II, when samples will be drawn immediately before the booster injection and at 7 days, 14 days, and 28 days post-booster injection (specificity and CMI at all time points and affinity at D0 and D28 post-booster).

Ab Specificity and Affinity Maturation

Ab Specificity

Sera will undergo a bead-based depletion method in a coordinated manner with the wild-type dengue parental strains (DENV01/3/4 and DENV02) and control bovine serum albumin (BSA) to qualitatively assess whether the neutralizing Abs elicited by the vaccine are primarily homotypic or cross-reactive heterotypic. Depletion will be confirmed by a Luminex-bead fluorescent based read-out that is similar to an ELISA but can assess responses to all 4 serotypes in a single sample run.

The neutralizing Abs in the depleted and BSA-control depleted sera will be analyzed by a flow cytometry-based neutralization assay using the U937 DC-SIGN cell line. Samples undergo a 3-fold serial dilution from 20-fold to 131,220 fold and run independently against all 4 parental wild-type viruses. The percent neutralization will be calculated and the values fitted to a sigmoidal curve in GraphPad Prism to determine the 50% neutralization titer. Neutralization titers of the DENV-depleted samples will be compared to the neutralization titers of the BSA-depleted samples to determine whether the neutralizing Ab response is homotypic or heterotypic.

Ab Affinity Maturation

Affinity measurements and Ab concentration will be read on the ForteBio Octet RED384. Ab binding curves will be generated by binding a serotype cross-reactive MAb to the optical fiber sensors followed by the capture of the individual parental wild-type dengue viruses. For kinetic analysis, the virus-coated sensors will be exposed to serially-diluted sera samples. The initial binding rates will be used to calculate the serum Ab concentration ($\mu\text{g/mL}$) based on established calibration curves. A global fit to a 1:1 binding model (Data analysis software, ForteBio) will be used to generate the equilibrium binding constants and the affinity constants (K_D , nM).

Dengue Neutralizing Abs

The immunogenicity assessment methods of dengue neutralizing Abs are assays, along with the same as those presented in Section 9.1.1.2.

CMI Responses

The Intracellular Cytokine Staining and B-cell ELISPOT tests will be performed by the Sponsor's Research Department in Marcy l'Etoile, France.

T-cell Response (Intracellular Cytokine Staining)

Intracellular Cytokine Staining can measure the T-cell immune response to a variety of antigens after short-term activation of peripheral blood mononuclear cells (PBMCs). Cells are incubated with antigens (pools of peptides from YF 17D or dengue viruses), an Ab directed against the degranulation marker CD107a, secretion inhibitors such as brefeldin A and monensin, allowing the intracellular accumulation of cytokines in activated cells. The cells will be stained with the surface markers CD3, CD4, CD8, CD45RA, CCR7 and, after fixation and permeabilization, the cells are stained for intracellular markers CD154, IFN- γ , TNF- α , IL2, and MIP-1beta. Cells are then analyzed by flow cytometry.

B-cell Response (ELISPOT B)

Antibody secreting cell (ASC) frequency will be measured by an ELISPOT assay adapted to measure dengue-specific responses. Briefly, nitrocellulose-bottomed 96-well plates will be coated with Dengue vaccine and incubated overnight at 4°C. After washing and blocking, PBMCs will be plated and incubated for 5 hours at 37°C. Plates will be washed and incubated with biotinylated mouse anti-human pan-IgG Fc Ab overnight at 4°C. Plates will be washed, incubated with peroxidase-conjugated streptavidin, and developed with substrate. Spots will be enumerated with an automated spot reader.

Dengue-specific B-cells memory responses will be evaluated after 5 days of PBMC polyclonal stimulation in vitro. After 5 days in culture, the cells will be recovered, washed, and used in the ELISPOT assay described above.

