4.3.1.2 Immunogenicity Assessment Methods

See Section 9.3.1.2 of the protocol.

The lower limit of detection (LLOD) for the 50% of neutralization titer by flow cytometry for Ab specificity is a titer of 20. To be able to calculate affinity, the LLOD for measuring the kinetic rates is an Ab concentration of 1 ng/mL and the lowest dissociation constant K_D that can reliably be measured on the instrument is 10 pM.

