Note: Undepleted is defined as BSA-control depleted sera and depleted is DENV depleted samples. Homotypic response is defined as a neutralizing antibody titer above 20 (1/dil) following DENV depletion.

- Serotype-specific affinity (KA, nM⁻¹) and Ab concentration (µg/mL) for each of the four parental dengue virus strains will be measured (at V01, V06, V07, and V10).

All the analyses will be descriptive at each available time point by treatment subgroups (Group 1a/1b/2a/2b/3a/3b), by subgroups in Y1 (Group 1a/2a/3a), by subgroups in Y2 (Group 1b/2b/3b) and by treatment groups (Group 1/2/3)..

- For categorical data, the number and percentage of subjects above or equal to the LLOD, and the 95% CI of the percentage of the subjects.
- For continuous data, Log10: mean and standard deviation; geometric mean, 95% CI of the geometric mean and quartiles, minimum and maximum value

As this objective is exploratory, other analyses might be performed.

Note: A total of 60 subjects (10 subjects in each of 6 subgroups) who consent to participate in additional immunological testing will also be included in a specific subset (AIT subset). The 1:1 ratio and 10 subjects per subgroup is unlikely to hold as only subjects dengue seropositive at baseline will be eligible to booster injection.

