5.7 Changes in the Conduct of the Trial or Planned Analyses

The following parts written in SAP are the changes different from Protocol Amendment 1:

The definition of j had been clarified for the Overall hypothesis.

The definition of WHO criteria and the corresponding derivation method had been added for virologically-confirmed dengue cases.

Instead of presenting the number and percentage of subjects with hospitalized suspected dengue case, only the hospitalized virologically-confirmed dengue cases will be summarized.

The ANCOVA model will be tested in Year 1 (Group 2a and Group 3a vs. Group 1a) and Year 2 (Group 2b and Group 3b vs. Group 1b).

The definition of depleted and undepleted for Ab specificity had been added: undepleted is defined as BSA-control depleted sera and depleted is DENV depleted samples.

The definition of homotypic Abs had been changed based on recent research findings to a neutralizing antibody titer above 20 (1/dil) following DENV depletion. Heterotypic antibodies will not be analyzed.

Delete “If non-inferiority is not achieved in Primary Objective, assessments of immunogenicity will be descriptive.” The descriptive analyses will conduct anyway regardless of the non-inferiority is achieved or not.

The definition of successful conclusion at Stage I and Stage II separately was added for clarity. Bonferroni adjustment for multiple testing at 28 days and 1 year post-Inj3 between Group 2 and Group 1 was removed and the adjustment of power was added as illustrated in Section 5.5.

The age stratus (9-16, 17-45 and 46-50 years of age) were added in definition of age group.

The definition of AUC-MB was added.

Description and comparison of GM in seropositive subjects between age strata were added, both overall and within each Group. These will allow the assessment of immunogenicity profile by age strata.

The ANCOVA model was added for 28 days after injection 3 between age strata adjusting for baseline neutralizing Ab levels.

The ANCOVA model was added for 28 days post-booster between age strata adjusting for the pre-booster neutralizing Ab levels.

6 References List

- 1 Newcombe R.G., Two-sided confidence intervals for the single proportion: comparison of seven methods, *Statistics in Medicine*, (1998) 17, 857-872

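### The SAP's homotypic rule (depleted titre above 20) shows that residual type-specific antibody is detectable; it cannot show whether a response is mainly homotypic

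*Protocol*

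**What the plan says.** **Protocol.** Section 9.3.1.2.2 gives the purpose of the specificity assay: "to qualitatively assess whether the neutralizing Abs elicited by the vaccine are primarily homotypic or cross-reactive heterotypic". Sera are depleted with the parental dengue strains or with BSA as control, and both are titrated. The same section gives the method: "Neutralization titers of the DENV-depleted samples will be compared to the neutralization titers of the BSA-depleted samples to determine whether" the response is homotypic or heterotypic. Section 9.3.1.1 defines homotypic antibody from values above the lower limit of quantitation "for the neutralizing titer and % of Ab remaining following depletion". It gives no numerical cut-off for the percentage remaining.

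**SAP.** Section 5.1.3.2 replaces this with one absolute criterion: "Homotypic response is defined as a neutralizing antibody titer above 20 (1/dil) following DENV depletion". Section 4.3.1.2 states that the lower limit of detection "for the 50% of neutralization titer by flow cytometry for Ab specificity is a titer of 20". Section 5.7 declares the change ("The definition of homotypic Abs had been changed based on recent research findings") and adds: "Heterotypic antibodies will not be analyzed".

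The BSA-control titre is still listed for assessment in SAP 5.1.3.2, under the label undepleted, but it plays no part in the classification. Specificity is listed there at V01, V06, V07, V08, V09 and V10. SAP 4.3.1.1 and 4.3.1.2 still refer to protocol 9.3.1.1 and 9.3.1.2, which contain the two-part definition and the comparison with control.

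**The concern.** The protocol's question is relative: of the neutralising antibody present, is most of it type-specific or cross-reactive? The SAP's rule is absolute. A serum with a high total titre can pass with a very small share remaining, and a serum with a low total titre can fail with half its titre remaining.

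Results are to be described by visit, by group and by subgroup. Where these differ in total titre, the percentage classed homotypic can differ even though the share remaining is the same. The risk is one of interpretation: a higher percentage after the booster, or in one schedule group, could be reported as a more type-specific response when the rule cannot show that.

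**Working it through.** **1. What the cut-off is.** Protocol 9.3.1.2.2 gives a 3-fold dilution series from 20 to 131,220. Check: 20 × 3^k for k = 0 to 8 gives 20, 60, 180, 540, 1,620, 4,860, 14,580, 43,740 and 131,220, which matches. The homotypic cut-off of 20 is therefore both the lowest dilution tested and the stated detection limit. The rule is a detectability rule.

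**2. How it depends on total titre.** Let T be the BSA-control titre and f the share remaining after DENV depletion. The depleted titre is f × T, so the rule is met when T > 20 / f.

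| f | T needed (20 / f) |
|---|---|
| 2% | 1,000 |
| 5% | 400 |
| 10% | 200 |
| 20% | 100 |
| 50% | 40 |

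**3. Single sera.**
- f = 5%: T = 200 gives 10, not homotypic; T = 800 gives 40, homotypic. In both, 95% of the titre is removed.
- The ordering can reverse. T = 2,000 with 2% remaining gives 40, homotypic; T = 35 with 50% remaining gives 17.5, not homotypic.

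**4. Group percentages.** The documents give neither f nor the distribution of T for this assay, so these are assumptions: log-normal T, f the same for all subjects and both visits, and a four-fold rise in geometric mean. Four-fold is borrowed from the seroconversion definition in SAP 4.4.1.2, which applies to PRNT. The percentage above 20 is 1 − Φ[(log10(20/f) − log10 GMT) / SD]. For f = 5% and SD 0.5: (2.602 − 2.301)/0.5 = 0.602 at GMT 200, giving 27.4%; (2.602 − 2.903)/0.5 = −0.602 at GMT 800, giving 72.6%.

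| f (SD 0.5) | GMT 200 | GMT 800 |
|---|---|---|
| 2% | 8.1% | 42.3% |
| 5% | 27.4% | 72.6% |
| 10% | 50.0% | 88.6% |

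Over SD 0.4 to 0.7, f 5% to 20% and starting GMT 100 to 400, the first percentage runs from 7% to 93% and the second from 50% to 99.9%. It rises in every case, with f unchanged.

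**5. Is a simple ratio enough?** Not if depleted titres below 20 are replaced by a fixed value. With f = 5%, GMT 200 and SD 0.5, about 73% of depleted titres (100 − 27.4) are at or below 20. Simulating the scenario of step 4 among subjects with BSA-control titre above 20 gives these geometric mean percentages remaining:

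| True f | Value substituted | GMT 200 | GMT 800 |
|---|---|---|---|
| 5% | 20 | 11.4% | 6.1% |
| 5% | 10 | 6.9% | 5.0% |
| 2% | 20 | 9.8% | 3.6% |
| 2% | 10 | 5.2% | 2.4% |

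The substituted ratio falls as total titre rises, again with f constant. A ratio therefore needs a censoring rule. SAP 4.4.1.1 covers values below the LLOQ and sets no rule for values below this assay's detection limit.

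**The case against.** The strongest reply has four parts.

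- **The rise may be real.** A reader might infer that the booster only seems to create type-specific antibody. The documents do not support that. If depletion removes the cross-reactive antibody, as the Luminex read-out in protocol 9.3.1.2.2 is meant to confirm, a residual going from 10 to 40 is a genuine rise in type-specific antibody. It would be an artefact only if depletion were incomplete. The protocol states no acceptance limit for that check, but nothing shows that it fails. This part stands.
- **The control titre is not discarded.** It is also tempting to say that the SAP ignores the BSA-control titre. That holds for the classification only. SAP 5.1.3.2 plans geometric means with confidence intervals and the percentage at or above the detection limit, so a reader could divide one geometric mean by the other. This stands in part: no paired ratio, interval or censoring rule is specified.
- **The change is declared, and the protocol's version was not operational.** Both are true, and the research findings cited in SAP 5.7 are not given, so their merit cannot be judged here. But declaring a detection rule does not make it a measure of specificity. The SAP's objective is still to describe specificity, and it still refers to the protocol sections containing the comparison.
- **Conditioning.** Restricting to subjects with a measurable control titre selects on a post-vaccination result. This stands, so such a table is descriptive and must show who was left out.

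**Conclusion.** The point holds as one of labelling and interpretation. The SAP's rule answers whether residual type-specific neutralising antibody is detectable. It does not answer whether a response is mainly homotypic or mainly cross-reactive, because it contains neither the control titre nor the percentage remaining. A higher percentage above 20 after the booster, or in one schedule group, must not be read as a shift in specificity.

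The dependence on total titre follows from the algebra for any fixed share above zero. Its size rests wholly on assumed values of share, geometric mean and SD, with no between-subject spread in the share. The 27% to 73% example is illustrative and not a forecast.

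The endpoint is exploratory and descriptive, in a subset of at most 60 subjects. No primary or secondary conclusion is affected.

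**What to change.** In SAP 5.1.3.2:

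1. Keep the above-20 rule and label it *homotypic antibody detectable*.
2. For each serotype and each specificity visit (V01, V06, V07, V08, V09, V10, where assayed), add the paired percentage remaining = 100 × DENV-depleted titre / BSA-depleted titre, among subjects whose BSA-depleted titre is above 20.
3. Treat depleted titres below 20 as left-censored, with no fixed value substituted. One option is a censored-normal estimate on the log10 ratio, with each subject's limit at log10(20 / BSA-depleted titre). Another is to report the number censored with those bounds.
4. Show separately the number with BSA-depleted titre at or below 20.
5. Base any statement that a response is mainly homotypic on the percentage remaining. If this is not wanted, restrict the stated objective to detection and amend the SAP's references to protocol 9.3.1.1 and 9.3.1.2 to match.

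Cost: SAP wording and one extra descriptive table. Both titres are already planned, so no new assay, sample or visit is needed. The downside is imprecise estimates where censoring is heavy, most likely at low-titre visits.
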